4.5.11.2 On Treatment

All treatment visits must occur within ± 3 days from the scheduled date unless otherwise noted (see [Appendix 1](#)). All procedures, tests, and assessments will be performed on the day of the specified visit unless a time window is specified. Assessments scheduled

on the day of study treatment administration (Day 1) of each cycle should be performed prior to study treatment infusion unless otherwise noted.

4.5.11.3 Treatment Discontinuation

Patients who discontinue study treatment will return to the clinic for a treatment discontinuation visit within 30 days after the last dose of study treatment. The visit at which the investigator determines a loss of clinical benefit may be used as the treatment discontinuation visit. In the event that the decision for discontinuation is due to an adverse event and this visit also shows progressive disease, discontinuation will be marked as due to progressive disease.

See the study flowcharts provided in [Appendix 1](#).

Patients who discontinue study treatment must be followed according to the follow-up visit schedule for progression and/or survival until death, loss to follow-up, or withdrawal of consent, which will be defined as study discontinuation.

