4.6.2 Study Treatment Discontinuation

Patients must discontinue study treatment if they experience any of the following:

- Disease progression (see Section 4.3.2.4 for dosing beyond progression)
- Symptomatic deterioration attributed to disease progression as determined by the investigator after integrated assessment of radiographic data, biopsy results, and clinical status
- Intolerable toxicity related to any study drug
- Any medical condition that may jeopardize the patient's safety if he or she continues study treatment
- Use of another non-protocol anti-cancer therapy (see Section 4.4.2)
- Pregnancy

Patients must provide written consent to acknowledge deferring any standard treatment options that may exist in favor of continuing treatment at the time of initial progression.

The primary reason for study drug discontinuation should be documented on the appropriate eCRF.

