5.2.1 Adverse Events

According to the ICH guideline for Good Clinical Practice, an adverse event is any untoward medical occurrence in a clinical investigation subject administered a pharmaceutical product, regardless of causal attribution. An adverse event can therefore be any of the following:

- Any unfavorable and unintended sign (including an abnormal laboratory finding), symptom, or disease temporally associated with the use of a medicinal product, whether or not considered related to the medicinal product
- Any new disease or exacerbation of an existing disease (a worsening in the character, frequency, or severity of a known condition), except as described in Section [5.3.5.10](#)
- Recurrence of an intermittent medical condition (e.g., headache) not present at baseline
- Any deterioration in a laboratory value or other clinical test (e.g., ECG, X-ray) that is associated with symptoms or leads to a change in study treatment or concomitant treatment or discontinuation from study drug
- Adverse events that are related to a protocol-mandated intervention, including those that occur prior to assignment of study treatment (e.g., screening invasive procedures such as biopsies)

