6.2 SUMMARIES OF CONDUCT OF STUDY

Enrollment, study drug administration, and discontinuation from the study will be summarized by treatment arm. The incidence of study drug discontinuation for reasons other than disease progression will similarly be tabulated. Protocol violations, including

major violations of inclusion/exclusion criteria, will be summarized in a similar manner by treatment arm.

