6.6 SAFETY ANALYSES

Safety analyses will be performed on the safety population and will include all randomized patients who received at least one dose of study drug. Summaries will be presented for the safety-evaluable population by treatment arm. For safety analyses, patients will be grouped according to whether any amount of atezolizumab or cobimetinib was received, including when atezolizumab or cobimetinib was received in error. For example, if a patient assigned to Arm C received either cobimetinib or atezolizumab in error, this patient will be grouped to Arm A or Arm B, respectively. If a patient assigned to Arm A received atezolizumab but no cobimetinib at all, then this patient will be grouped to Arm B.

Study drug exposure, including treatment duration, number of doses, and dose intensity, will be summarized for each treatment arm using descriptive statistics.

Verbatim description of adverse events will be mapped to MedDRA thesaurus terms and graded according to NCI CTCAE v4.0. All adverse events that occur during or after the first study drug dose will be summarized by treatment arm and NCI CTCAE grade.

In addition, serious adverse events, severe adverse events (Grade 3, 4, and 5), adverse

events of special interest, and adverse events leading to study drug discontinuation or interruption will be summarized accordingly. Multiple occurrences of the same event will be counted once at the maximum severity. The proportion of patients who experience at least one adverse event will be reported by toxicity term and treatment arm.

Deaths reported during the study treatment period and those reported during the follow-up period after treatment discontinuation will be summarized by treatment arm.

Laboratory data with values outside the normal ranges will be identified. In addition, selected laboratory data and vitals will be summarized by treatment arm.

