4.2 ANALYSIS OF STUDY CONDUCT

Study enrollment, major protocol deviations including major deviations of inclusion/exclusion criteria, and reasons for study termination will be summarized overall and by treatment arm for the ITT population. Study treatment administration and reasons for discontinuation from study treatment will be summarized for the Safety population.

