4.6.2 Adverse Events

Verbatim description of AEs will be mapped to MedDRA thesaurus terms and graded according to NCI CTCAE v4.0. All AEs that occur during or after the first study drug dose will be summarized by treatment arm and NCI CTCAE grade. In addition, serious adverse events (SAE), severe AEs (Grades 3, 4, and 5), AEs of special interest, and AEs leading to study drug discontinuation or interruption will be summarized accordingly. Multiple occurrences of the same event will be counted once at the maximum severity. The proportion of patients who experience at least one AE will be reported by toxicity term and treatment arm.

Listings of AEs will include all AEs with an onset that occurred on or after the first study drug treatment up to the data cutoff date.

Deaths reported during the study treatment period and those reported during the follow-up period after treatment discontinuation will be summarized by treatment arm.

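### Marking AE-decided discontinuations as progression when the visit also shows PD makes the reason-for-discontinuation summaries undercount AE-driven stopping within each arm

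*Protocol*

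**What the plan says.** Protocol 4.5.11.3 brings patients who stop treatment back for a "treatment discontinuation visit within 30 days after the last dose of study treatment". It then rules on how the stop is coded when two causes are present: "discontinuation is due to an adverse event and this visit also shows progressive disease, discontinuation will be marked as due to progressive disease". Protocol 4.6.2 asks for one reason: "The primary reason for study drug discontinuation should be documented on the appropriate eCRF". Neither document describes a field for a second reason or a table of patients to whom both reasons apply.

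Two planned summaries rest on the reason for stopping:

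- Protocol 6.2, by arm: "The incidence of study drug discontinuation for reasons other than disease progression will similarly be tabulated".
- SAP 4.2: "reasons for discontinuation from study treatment will be summarized for the Safety population". That sentence does not itself repeat the words on treatment arm.

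A third summary is planned separately in the safety sections. In Protocol 6.6, "adverse events leading to study drug discontinuation or interruption will be summarized accordingly"; in SAP 4.6.2, "AEs leading to study drug discontinuation or interruption will be summarized accordingly". Neither says whether it is derived from the adverse event record or from the marked reason for discontinuation.

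**The concern.** The rule first accepts that an adverse event drove the decision and then directs the site to record something else. That conflicts with the request in Protocol 4.6.2 for the primary reason, and the recoded value feeds planned summaries. An affected patient drops out of the count of non-progression discontinuations and appears under progression in the table of reasons.

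Safety against regorafenib is a stated objective (Protocol 2.2), and Protocol 3.3 gives the need for better-tolerated treatment as part of the rationale. A reader who takes the reason tables as a measure of tolerability would see too few AE-driven stops. If the safety summary of AEs leading to discontinuation comes from the adverse event record, the study report could also carry two different counts of such stops, with no rule for reconciling them.

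**Working it through.** **Step 1: follow one patient through the rules.** Treatment is stopped because of an adverse event, and the discontinuation visit shows PD.

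- Primary reason under Protocol 4.6.2: adverse event.
- Marked reason under Protocol 4.5.11.3: progressive disease.
- Protocol 6.2 count of non-progression discontinuations: patient absent.
- SAP 4.2 reasons: patient listed under progression.
- Protocol 6.6 and SAP 4.6.2 summary: patient present if it is built from the adverse event record, absent if it is built from the marked reason.

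**Step 2: inputs.** The documents state no discontinuation rate and no overlap rate, so there is no planned figure to reproduce. From the documents: about 180 patients in Arm A and 90 in each of Arms B and C (Protocol 3.1), scans every 8 weeks (56 days), and a discontinuation visit up to 30 days after the last dose. Assumed: *p*, the true proportion of an arm stopping for an AE, 5% to 20%; and *q*, the share of those whose visit also shows PD, 10% to 50%.

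**Step 3: effect within an arm.** Proportion shown = p × (1 − q).

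| p | q = 10% | q = 30% | q = 50% |
|---|---|---|---|
| 5% | 4.5% | 3.5% | 2.5% |
| 10% | 9% | 7% | 5% |
| 20% | 18% | 14% | 10% |

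For p = 20% in an arm of 180, 36 true AE-driven stops appear as 36 × 0.9 = 32.4, 36 × 0.7 = 25.2 or 36 × 0.5 = 18. The SAP summary uses treated patients, so the actual denominator could be slightly smaller. The error is always downward and is zero only if q = 0.

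**Step 4: rough size of q.** If stopping times fall evenly across the scan cycle and the visit uses the whole window, a scheduled scan falls inside it for about 30/56 = 54% of patients. If 20% to 60% of those scans show PD (assumed), q = 0.536 × 0.20 = 11% to 0.536 × 0.60 = 32%. Earlier visits lower this; unscheduled scans, which Protocol 4.5.5 allows, raise it.

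**Step 5: effect on the difference between arms.** Take true rates of 20% and 10%, a difference of 10 points.

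- q = 10% in both arms: 0.20 × 0.9 − 0.10 × 0.9 = 9 points.
- q = 30% in the first, 10% in the second: 0.20 × 0.7 − 0.10 × 0.9 = 5 points.
- q = 10% in the first, 30% in the second: 0.20 × 0.9 − 0.10 × 0.7 = 11 points.

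The contrast can shrink or grow, depending on which arm has more overlap.

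**The case against.** The best defence is that this is a precedence convention. With one reason recorded and two that apply, some rule is needed; this one is set in advance and is the same in every arm, and PD is itself a stopping criterion. That stands only in part. Protocol 4.3.2.4 allows treatment beyond RECIST progression in all arms when its conditions are met, so PD at the visit does not show that treatment would have stopped. The visit may also come up to 30 days after the last dose, so PD first seen after a toxicity stop can overwrite the reason for it.

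The second defence is that toxicity-driven stopping is read mainly from the summary of AEs leading to discontinuation. This carries weight. The rule governs only how the discontinuation is marked. Nothing in it removes or re-attributes the event, and the AE definition in Protocol 5.2.1 includes a worsened laboratory or other test result that "leads to a change in study treatment or concomitant treatment or discontinuation from study drug". A reader might infer that every planned table of toxicity-driven stopping is understated; the documents do not show the rule reaching this one. Its unstated source supports a request for clarification, no more.

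Three further limits stand. Protocol 5.1.4.2 (Table 4) lets one drug in Arm A stop for toxicity while the other continues, which on its face does not trigger the rule. The discontinuation rate is not among the safety outcome measures in SAP 2.2.6. No formal test uses the field.

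**Conclusion.** The concern holds for the reason-for-discontinuation summaries in Protocol 6.2 and SAP 4.2. Followed as written, the rule undercounts AE-driven discontinuation within each arm whenever an AE-decided stop and PD coincide. The size cannot be determined from the documents. The illustrated fall, from 20% to between 18% and 10%, rests wholly on assumed rates and on every AE-driven stop being open to recoding, which may be too many in Arm A.

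A reader might also infer that the bias favours the more toxic regimen. The documents do not support that: no figure in them shows which arm has more overlap, and Step 5 shows the difference moving either way. The summary in Protocol 6.6 and SAP 4.6.2 is affected only if it is built from the recoded reason. The primary OS analysis is untouched. The rule is still worth correcting, because it gives a wrong entry in planned tolerability summaries and is cheap to change.

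**What to change.** 1. Replace the sentence in Protocol 4.5.11.3 so that the reason that drove the decision is recorded as primary, in line with Protocol 4.6.2, and concurrent PD is captured as a second reason or a flag.
2. In the Protocol 6.2 and SAP 4.2 summaries, add a row by arm for patients with both an AE-decided stop and concurrent PD.
3. State in SAP 4.6.2 that the summary of AEs leading to discontinuation is derived from the adverse event record, whatever reason is marked.

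The cost is one protocol sentence, one eCRF field or completion guideline, one SAP line and one extra table row. The change affects recording and tabulation only; it does not alter when or why treatment is stopped.

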4.5.11.4 Follow-Up

After the treatment discontinuation visit, adverse events should be followed as outlined in Section 5.6. For patients who discontinue study treatment for reasons other than disease progression, tumor assessments should continue to be performed as scheduled (i.e., every 8 weeks \pm 1 week) until patient death or documented disease progression.

Survival follow-up should continue until death, withdrawal of consent, the patient is lost to follow-up, or study termination by the Sponsor, whichever occurs first. If the patient withdraws from study, the study staff may use a public information source (e.g., county records) when permissible, to obtain information about survival status only.

See the study flowcharts provided in [Appendix 1](#) for assessments to be performed during follow-up visits.

4.5.11.5 Unscheduled Visits

Assessments for unscheduled visits related to a patient's underlying CRC, study treatment, or adverse events should be performed as clinically indicated and entered into Unscheduled Visit eCRFs.

4.6 PATIENT, TREATMENT, STUDY, AND SITE DISCONTINUATION

4.6.1 Patient Discontinuation

Patients have the right to voluntarily withdraw from the study at any time for any reason. In addition, the investigator has the right to withdraw a patient from the study at any time. Reasons for withdrawal from the study may include, but are not limited to, the following:

- Patient withdrawal of consent at any time
- Any medical condition that the investigator or Sponsor determines may jeopardize the patient's safety if he or she continues in the study

- Investigator or Sponsor determines it is in the best interest of the patient
- Patient non-compliance

Every effort should be made to obtain information on patients who withdraw from the study. The primary reason for withdrawal from the study should be documented on the appropriate eCRF. However, patients will not be followed for any reason after consent has been withdrawn. Patients who withdraw from the study will not be replaced.

4.6.2 Study Treatment Discontinuation

Patients must discontinue study treatment if they experience any of the following:

- Disease progression (see Section 4.3.2.4 for dosing beyond progression)
- Symptomatic deterioration attributed to disease progression as determined by the investigator after integrated assessment of radiographic data, biopsy results, and clinical status
- Intolerable toxicity related to any study drug
- Any medical condition that may jeopardize the patient's safety if he or she continues study treatment
- Use of another non-protocol anti-cancer therapy (see Section 4.4.2)
- Pregnancy

Patients must provide written consent to acknowledge deferring any standard treatment options that may exist in favor of continuing treatment at the time of initial progression.

The primary reason for study drug discontinuation should be documented on the appropriate eCRF.

4.6.3 Study and Site Discontinuation

The Sponsor has the right to terminate this study at any time. Reasons for terminating the study may include, but are not limited to, the following:

- The incidence or severity of adverse events in this or other studies indicates a potential health hazard to patients.
- Patient enrollment is unsatisfactory.

The Sponsor will notify the investigator if the Sponsor decides to discontinue the study.

The Sponsor has the right to close a site at any time. Reasons for closing a site may include, but are not limited to, the following:

- Excessively slow recruitment
- Poor protocol adherence
- Inaccurate or incomplete data recording

- Non-compliance with the International Conference on Harmonisation (ICH) guideline for Good Clinical Practice
- No study activity (i.e., all patients have completed the study and all obligations have been fulfilled)

5. ASSESSMENT OF SAFETY

In the United States, atezolizumab is approved for the treatment of locally advanced or metastatic urothelial bladder cancer who have progressed during or following platinum-containing chemotherapy and for metastatic non–small cell lung cancer who have progressed during or following platinum-containing chemotherapy and if harboring an EGFR or ALK aberration have progressed on U.S. Food and Drug Administration-approved therapy for these aberrations and is currently in clinical development for other indications. The safety plan is based on results from nonclinical studies, completed and ongoing clinical studies, and published data on similar molecules. Please refer to the atezolizumab Investigator's Brochure for a complete summary of safety information.

Cobimetinib (for use with vemurafenib) is approved in the United States and European Union as well as other countries for the treatment of metastatic melanoma. The safety plan for patients in this study is based on clinical experience with cobimetinib in completed and ongoing studies. The anticipated important safety risks for cobimetinib are outlined below. Please refer to the cobimetinib Investigator's Brochure for a complete summary of safety information.

Regorafenib is approved in the United States, European Union, and Japan. Please refer to the Stivarga (regorafenib) Prescribing Information for a complete summary of safety information.

Several measures will be taken to ensure the safety of patients who participate in this study. Eligibility criteria have been designed to exclude patients at higher risk for toxicities. Patients will undergo safety monitoring during the study, including assessment of the nature, frequency, and severity of adverse events. In addition, guidelines for managing adverse events, including criteria for dosage modification, and treatment interruption or discontinuation, are provided below. There are separate guidelines for the three different arms as the toxicities and management guidelines are distinct for the three different arms. Please refer to the specific guidelines for each arm individually.

5.1 SAFETY PLAN

The risks associated with cobimetinib, atezolizumab, and regorafenib are detailed in Section 5.1.1, Section 5.1.2, and Section 5.1.3, respectively.

5.1.1 Risks Associated with Cobimetinib

Information related to risks attributed to cobimetinib is based on safety data from Phase III Study GO28141 (cobimetinib plus vemurafenib), Phase Ib Study NO25395 (cobimetinib plus vemurafenib), and Phase I Study MEK4592g (cobimetinib monotherapy). For further information regarding clinical safety, please refer to the current cobimetinib Investigator's Brochure.

5.1.1.1 Important Identified Risks Associated with Cobimetinib Hemorrhage

Hemorrhage, including major hemorrhages defined as symptomatic bleeding in a critical area or organ, can occur with cobimetinib. In clinical studies with cobimetinib, events of cerebral hemorrhage, gastrointestinal tract hemorrhage, reproductive tract hemorrhage, and hematuria, have been reported.

In the Phase III Study GO28141, Grade 1–4 hemorrhagic events were reported in 13.0% of patients treated with cobimetinib plus vemurafenib, and in 7.3% of patients treated with placebo plus vemurafenib. The majority of hemorrhagic events were Grade 1 or 2 and non-serious. Grade 3–4 hemorrhage events were reported in 1.2% of patients receiving cobimetinib plus vemurafenib and 0.8% of patients receiving placebo plus vemurafenib.

Caution should be used in patients with additional risk factors for bleeding, such as brain metastases, and/or in patients that use concomitant medications that increase the risk of bleeding (including antiplatelet or anticoagulant therapy).

Instructions for dose modification for hemorrhage events are included in [Appendix 3](#).

Serous Retinopathy

Serous retinopathy (fluid accumulation within the layers of the retina) has been observed in patients treated with MEK-inhibitors, including cobimetinib ([Flaherty et al. 2012](#)). Manifestations of serous retinopathy include visual disturbances, findings of retinal detachment, and retinopathy. Serous retinopathy events may also be asymptomatic.

Serous retinopathy has been characterized in the Phase III Study GO28141. The study incorporated prospective serial ophthalmic examinations for all enrolled patients. Serous retinopathy was reported more frequently in patients treated with cobimetinib plus vemurafenib than placebo plus vemurafenib (25.5% vs. 2.8%, respectively), and approximately half the events were asymptomatic Grade 1 events. Few patients treated with cobimetinib plus vemurafenib experienced Grade ≥ 3 ocular events (2.8%); the majority of these were managed with dose modification of both cobimetinib and vemurafenib.

To address serous retinopathy with cobimetinib treatment, all patients are required to undergo a baseline ophthalmologic examination to assess for history or evidence of

retinal pathology that is considered to be a risk factor for or indicative of neurosensory retinal detachment, central serous chorioretinopathy, neovascular retinopathy, or retinopathy of prematurity. Patients will also undergo ophthalmologic examinations at specified time points throughout the study (see [Appendix 1](#)). Details regarding baseline and subsequent ophthalmologic examinations are provided in [Appendix 3](#).

Guidelines for management of patients who develop Grade ≥ 2 visual disorders or retinopathy are provided in [Appendix 3](#).

Left Ventricular Dysfunction

Decrease in left ventricular ejection fraction from baseline has been reported in patients receiving cobimetinib. Left ventricular dysfunction may occur with signs and symptoms of cardiac failure, or reduction in left ventricular ejection fraction events may be asymptomatic.

Left ventricular dysfunction has been characterized in the Phase III Study GO28141. The study incorporated prospective serial left ventricular ejection fraction evaluation in all patients. With active surveillance, measured reductions in left ventricular ejection fraction were observed more frequently in patients treated with cobimetinib plus vemurafenib than placebo plus vemurafenib (8.5% vs. 3.7%, respectively, of Grade 2 or 3 decrease). Of the patients treated with cobimetinib plus vemurafenib, 2 patients (0.8%) had symptomatic reduction in left ventricular ejection fraction and the remaining patients were asymptomatic. Most left ventricular ejection fraction reduction events in patients on cobimetinib plus vemurafenib (62%) improved or resolved with management according to the dose-modification guidelines (see [Appendix 3](#)).

Rhabdomyolysis and CPK Elevations

Elevations in CPK have been observed in patients who received cobimetinib monotherapy as well as when administered with other agents. The majority of CPK elevations reported were asymptomatic, non-serious, and resolved with or without study drug interruption. One event of rhabdomyolysis was reported in the Phase III Study GO28141 (cobimetinib plus vemurafenib), and rhabdomyolysis has been reported in postmarketing experience.

In Study GO28141, elevated CPK was reported as an adverse event more frequently in patients treated with cobimetinib plus vemurafenib (32.4% all grades, 11.3% Grade ≥ 3 events) than placebo plus vemurafenib (8.1% all grades, 0% Grade ≥ 3 events).

CPK will be monitored at baseline and monthly during treatment or as clinically indicated. Instructions for Dose Modification for elevated CPK and rhabdomyolysis are included in [Appendix 3](#).

Photosensitivity (when Administered with Vemurafenib)

No evidence of phototoxicity has been observed with cobimetinib as a single agent. However, photosensitivity was observed on the GO28141 trial with a higher frequency in the cobimetinib plus vemurafenib arm versus placebo plus vemurafenib arm (46.3% vs. 35.4%, respectively). The majority of events were Grades 1 or 2, with Grade ≥ 3 events occurring in 3.6% of patients in the cobimetinib plus vemurafenib arm versus 0% in the placebo plus vemurafenib arm. Grade ≥ 3 photosensitivity events in the cobimetinib plus vemurafenib arm were primarily treated with topical medication in conjunction with interruption of study agents.

Pneumonitis

Events of pneumonitis have been reported in cobimetinib clinical studies. Most reported events were considered non-serious and low-severity grade. In the Phase III Study GO28141, pneumonitis events were reported more frequently in patients treated with cobimetinib plus vemurafenib than placebo plus vemurafenib (1.6% vs. 0.4%, all grades). There were no reported Grade ≥ 3 events in either study arm. Serious events were reported in 2 patients (0.8%) treated with cobimetinib plus vemurafenib. *Refer to [Appendix 3](#) for pneumonitis management guidelines.*

5.1.1.2 Potential Risks Associated with Cobimetinib Liver Laboratory Abnormalities and Severe Hepatotoxicity

Liver laboratory test abnormalities, including increases in ALT, AST, and alkaline phosphatase have been reported as adverse events and serious adverse events in patients treated with cobimetinib plus vemurafenib.

In the Phase III Study GO28141, liver laboratory test abnormalities reported as Grade ≥ 3 adverse events occurred more frequently in patients treated with cobimetinib plus vemurafenib than placebo plus vemurafenib (20.5% vs. 15.1%, respectively).

Generally, elevations in liver laboratory tests were managed effectively with dose modification guidelines. In both study arms, the majority of Grade ≥ 3 liver laboratory test abnormalities resolved. *Refer to [Appendix 3](#) for hepatotoxicity management guidelines.*

Impaired Female Fertility and Developmental Toxicity

There is a potential for effects on fertility and embryo-fetal toxicity based on results from nonclinical studies.

While no dedicated fertility studies have been conducted with cobimetinib in animals, degenerative changes observed in reproductive tissues included increased apoptosis/necrosis of corpora lutea and seminal vesicle, epididymal and vaginal epithelial cells in rats, and epididymal epithelial cells in dogs. These changes were reversible upon discontinuation of cobimetinib administration.

In a dedicated embryo-fetal toxicity study, cobimetinib produced fetal toxicity (resorptions and reductions in fetal weight), and teratogenicity (malformations of the great vessels

and skull) at similar systemic exposures to those observed in patients administered the 60 mg dose.

